4.2.2.1. Visit Windowing and Multiple Measurements at One Analysis Timepoint

Visit windowing for the primary end-point will be applied as specified in [Table 2](#) and [Table 3](#), and the windowed results will be used to determine the primary endpoint of SVR. Unscheduled assessments will be included in the analysis window. No imputation of missing data will be performed prior to visit windowing.

If there are multiple values within an analysis window the following rules will be applied:

For the end of GSK3228836 treatment and PegIFN treatment analysis timepoints, the latest available assessment in the window will be selected, with the worst non-missing value chosen first. The worst case ordering is as follows:

1. No Virologic Response
2. Missing due to WDE¹
3. Virologic Response
4. Missing (unrelated to WDEs)

For post end of sequential treatment analysis timepoints:

1. Worst non-missing value in the analysis window will be selected.
 - a) If values are the same, then the value closest to target day will be selected. If there are multiple values equidistant from the target day, the earliest will be selected.
 - b) If all values within an analysis window are missing, then the result is missing for the analysis window.
2. Worst value is defined in the order of highest actual value, then <LLOQ, and then TND.

¹ Missing due to WDE will be considered based on whether original value for the assessment is missing or is a non-response. If the original value at an assessment is 'No Virologic Response' prior to imputation for WDEs, then the assessment will be classified as 'Missing due to WDEs'. If the original value at an assessment is 'Missing' prior to imputation for WDEs, then the preceding non-missing value within the window will be selected.

Table 2 Primary Endpoint Analysis Visit Windows for Arm 1

Analysis Set	Parameter	Target Study Day	Analysis Window		Analysis Timepoint	Protocol Visit
			Beginning Timepoint	Ending Timepoint		
Efficacy	HBsAg and HBV DNA	162	148	Minimum of (182, PegIFN First Dosing Study day)	End of GSK3228836 treatment	Week 24
Efficacy	HBsAg and HBV DNA	330	295	350	End of PegIFN treatment / EoT	Week 48
Efficacy	HBsAg and HBV DNA	386	351	406	Post PegIFN treatment Week 8	Off-treatment Week 8
Efficacy	HBsAg and HBV DNA	456	407	462	Post PegIFN treatment Week 18	Off-treatment Week 18
Efficacy	HBsAg and HBV DNA	498	463	518	Post PegIFN treatment Week 24	Off-treatment Week 24

Table 3 Primary Endpoint Analysis Visit Windows for Arm 2

Analysis Set	Parameter	Target Study Day	Analysis Window		Analysis Timepoint	Protocol Visit
			Beginning Timepoint	Ending Timepoint		
Efficacy	HBsAg and HBV DNA	78	64	Minimum of (98, PegIFN First Dosing Study day)	End of GSK3228836 treatment	Week 12
Efficacy	HBsAg and HBV DNA	246	211	266	End of PegIFN Treatment / EoT	Week 36
Efficacy	HBsAg and HBV DNA	302	267	322	Post PegIFN treatment Week 8	Off-treatment Week 8
Efficacy	HBsAg and HBV DNA	372	323	378	Post PegIFN treatment Week 18	Off-treatment Week 18
Efficacy	HBsAg and HBV DNA	414	379	434	Post PegIFN treatment Week 24	Off-treatment Week 24

The primary analysis will be based on planned end of treatment regardless of whether a patient discontinued treatment.

For the first and second supplementary estimands described in Section 4.2.4.1 and Section 4.2.4.2, SVR will be measured from actual rather than planned end of treatment and the analysis windows should be amended accordingly. For these estimands, the date of last dose should be treated as the reference date and the rules in Table 4 should be used to determine the endpoint of SVR.

Table 4 Supplementary Endpoint Analysis Visit Windows for Arm 1 and Arm 2

Analysis Set / Domain	Parameter	Reference Day	Analysis Window		Analysis Timepoint
			Beginning Timepoint	Ending Timepoint	
Efficacy	HBsAg and HBV DNA	Reference date	Reference date - 35	Reference date + 20	End of Actual treatment
Efficacy	HBsAg and HBV DNA	Reference date + 56	Reference date + 21	Reference date + 76	Post treatment Week 8
Efficacy	HBsAg and HBV DNA	Reference date + 126	Reference date + 77	Reference date + 132	Post treatment Week 18
Efficacy	HBsAg and HBV DNA	Reference date + 168	Reference date + 133	Reference date + 188	Post treatment Week 24

If all analysis windows have non-missing response information, a participant's response (Responder or Non-responder) is determined as follows:

1. If rescue medication was used during on-treatment or off-treatment period, then the participant is a non-responder.
2. If HBsAg <LLOQ and HBV DNA <LLOQ in each of the analysis windows, then the participant is a responder, otherwise the participant is non-responder.
3. A result of TND is considered as <LLOQ.

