1.2. Schema

1.3. Schedule of Activities (SoA)

Both treatment arms will use the same Screening Table ([Table 1](#)). Separate tables have been produced for the GSK3228836 treatment period ([Table 2](#) and [Table 3](#)). Both treatment arms will use the same PegIFN Treatment Table ([Table 4](#)), Reassessment of PegIFN Eligibility Tables ([Table 5](#) and [Table 6](#); only required if participant is ineligible to start PegIFN as per [Table 4](#)) and Off Treatment Follow-up Table ([Table 7](#)).

[China specific Schedule of Activities can be found in [Appendix 7: Country-specific requirements](#)]

Instructions that are applicable to all treatment arms include:

- In selected countries/sites, participants will have the option to use a centralised home nursing provider. Only selected visits will have the option to be performed as a home visit, these will include drug administration, blood draws, participant assessments and data collection. The full specifications of the home nursing services will be outlined in the Study Reference Manual (SRM).
- Haematology (platelet count) will be analysed at a local laboratory prior to each GSK3228836 dose. The blood draw can be taken the day before GSK3228836 dosing. Results must be available prior to dosing. Haematology samples will be collected for central laboratory assessments in parallel. After GSK3228836 treatment is completed, haematology is only collected centrally on weeks of clinic visits.
- If a participant is not eligible to start PegIFN, eligibility will be reassessed. If the participant does not become eligible after 13 weeks, PegIFN will not be initiated in order to ensure participants receive at least 12 weeks of PegIFN treatment. Irrespective of the week that a participant starts PegIFN, the final dose will be given on Study Week 48 for Arm 1 and Week 36 for Arm 2 ([Figure 1](#)).
- PegIFN dosing maybe self-administered at home, where local regulations allow at the visits indicated in the SoA ([Table 4](#)).

Figure 1 Schematic of Planned GSK3228836 and PegIFN Dosing Periods and Off Treatment Follow-up Period

[figure not shown]

Table 1 Screening (All Treatment Arms)

ASSESSMENTS	
Informed Consent (obtained any time prior to screening)	X
Inclusion and exclusion criteria	X
Demography	X
Medical history (includes substance usage) and current medical conditions	X
Medication history and concomitant medication review	X
Full physical exam including height and weight	X
Vital signs	X

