If all HBsAg and HBV DNA data within the analysis window for the EOT visit is missing due to a WDE, and the participant withdraws from the study due to the WDE, the participant will be classified as not reaching EOT at follow-up. Data after the intercurrent event will be set to missing, and their SVR response will be imputed assuming missing at random using all available data from participants for whom SVR can be assessed.

If all HBsAg and HBV DNA data within the analysis window for the EOT visit is missing due to a WDE, but the participant later returns to study and has non-missing data in an analysis window, the data will be handled in the following two ways:

1. For observed VR responders, the data will be analysed as collected (treatment policy). No imputation of missing data will be performed.
2. For observed VR non-responders, data collected after the intercurrent event will be set to missing. Their SVR response will be imputed assuming missing at random using all available data from participants for whom SVR can be assessed (hypothetical strategy).

If all HBsAg and HBV DNA data within an analysis window after the planned end of sequential treatment (EoT) is missing unrelated to wide disruptive events, missing data will be considered as an SVR non-responder. No imputation of missing data will be performed.

If all HBsAg and HBV DNA data within an analysis window after the planned end of sequential treatment (EoT) is missing due to wide disruptive events, the participant's SVR status will be considering as missing due to WDE. Data after the intercurrent event will be set to missing, and the SVR response will be imputed using all available data from participants for whom SVR can be assessed.

If the participant has any HBsAg \geq LLOQ or HBV DNA \geq LLOQ or rescue medication usage at or after the planned end of sequential treatment (EoT), the subject will be classified as an SVR non-responder. No imputation of missing data will be performed.

If a participant has any assessments that are affected by a wide disruptive event, but the participant's HBsAg and HBV DNA within an analysis window are collected and the participant is a VR responder, the subject will be classified as an SVR responder.

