6.2.8. Assessment Windows for Early Termination

Unless otherwise specified, no windowing will be applied to unscheduled visits. Planned time relative to dosing will be used in figures, summaries, statistical analyses, and calculation of any derived parameters, unless otherwise stated. Unscheduled visits will not be included in summary tables and/or figures except from determining response for primary endpoint as described in Section 4.2.2 and summaries over “any time on treatment” or “any visit post-baseline”. Unscheduled visits will be included in listings.

Laboratory and vital signs data collected at Early Termination Visits will be assigned to assessment windows, according to the actual date.

Table 19 Early Termination Visit Windowing

Analysis Set / Domain	Target study day	Analysis Window		Analysis Timepoint
		Start day	End day	
GSK3228836 Arm 1 and Arm 2				
Lab, Vital Signs	1	1	2	Week 1 Day 1
	4	3	6	Week 1 Day 4
	8	7	9	Week 2 Day 8
	11	10	12	Week 2 Day 11
	15	13	18	Week 3 Day 15
	22	19	25	Week 4 Day 22
	$1+7*(x-1)$	$1+7*(x-1)-3$	$1+7*(x-1)+3$	Week x Day $1+7*(x-1)$
PegIFN Arm 1 Dosing Weeks*				
Lab Vital Signs	$1+7*(23+y+z)$	$1+7*(23+y+z)-3$	$1+7*(23+y+z)+3$	PegIFN Dosing Week y Day 1
PegIFN Arm 2 Dosing Weeks*				
Lab Vital Signs	$1+7*(11+y+z)$	$1+7*(11+y+z)-3$	$1+7*(11+y+z)+3$	PegIFN Dosing Week y Day 1
PegIFN Arm 1 Eligibility (No Dosing) Weeks (up to 13)				
Lab Vital Signs	$1+7*(23+u)$	$1+7*(23+u)-3$	$1+7*(23+u)+3$	PegIFN Eligibility Week u Day 1
PegIFN Arm 2 Eligibility (No Dosing) Weeks (up to 13)				
Lab Vital Signs	$1+7*(11+u)$	$1+7*(11+u)-3$	$1+7*(11+u)+3$	PegIFN Eligibility Week u Day 1

Analysis Set / Domain	Target study day	Analysis Window		Analysis Timepoint
		Start day	End day	
PegIFN Arm 1 No Dosing Assessment Weeks (week 14 onwards)				
Lab Vital Signs	$1+7*(23+v)$	$1+7*(23+v)-3$	$1+7*(23+v)+3$	PegIFN Assessment Week v
PegIFN Arm 2 No Dosing Assessment Weeks (week 14 onwards)				
Lab Vital Signs	$1+7*(11+v)$	$1+7*(11+v)-3$	$1+7*(11+v)+3$	PegIFN Assessment Week v
Off-Treatment Week (OTW) Follow-up Arm 1				
Lab Vital Signs	337	334	340	Off-Treatment Week 1
	344	341	347	Off-Treatment Week 2
	358	348	372	Off-Treatment Week 4
	386	373	400	Off-Treatment Week 8
	414	401	435	Off-Treatment Week 12
	456	436	477	Off-Treatment Week 18
	498	478	518	Off-Treatment Week 24
Off-Treatment Week (OTW) Follow-up Arm 2				
Lab Vital Signs	253	250	256	Off-Treatment Week 1
	260	257	263	Off-Treatment Week 2
	274	264	288	Off-Treatment Week 4

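### SAP 4.2.2.1: the EoT window includes the first two off-treatment visits and its selection rule can be read two ways, so EoT response, and SVR in a narrow subset, depend on the reading programmed

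*SAP*

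**What the plan says.** - **Window.** SAP Tables 2 and 3 give target day, first day and last day as "330 295 350 End of PegIFN treatment / EoT" (Arm 1) and "246 211 266 End of PegIFN Treatment / EoT" (Arm 2). Table 4 uses the same −35 to +20 days around the actual last dose for the first two supplementary estimands.
- **Selection at EoT.** SAP 4.2.2.1 states that "the latest available assessment in the window will be selected, with the worst non-missing value chosen first". It then ranks four categories from worst to best: non-response, missing due to a wide disruptive event (WDE), response, other missing. For the windows after EoT the rule is simply the worst non-missing value.
- **Calendar.** Under Protocol 1.3, "the final dose will be given on Study Week 48 for Arm 1 and Week 36 for Arm 2". Protocol Table 7 puts Off-Treatment Week 1 (OTW1) 7 days after the dosing period and draws HBsAg and HBV DNA at every off-treatment visit. SAP Table 19 agrees: "337 334 340 Off-Treatment Week 1".
- **Role in SVR.** SAP 4.2 and 4.2.2.1 require results below LLOQ in every window, EoT included. SAP 4.2.2.2 adds that with any HBsAg or HBV DNA value at or above LLOQ, or "rescue medication usage at or after the planned end of sequential treatment (EoT), the subject will be classified as an SVR non-responder".
- **Protocol data span.** Protocol 9.4.2 assesses the primary endpoint on data starting in the week treatment ends.
- **Relapse.** SAP 4.1.3.1 looks for relapse only after the relevant window has closed.

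**The concern.** A single sentence gives both *latest* and *worst* as the way to pick the EoT value, in a window of 56 days that covers on-treatment and off-treatment samples. The two readings can select different samples, and each has an unwanted result. *Latest* reads an end-of-treatment status from an off-treatment visit. *Worst* reaches back into treatment, before the period the protocol uses.

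The EoT result is one of the windows needed for SVR. It is also a secondary endpoint (SAP 4.3.1.1) and supplies the virologic-response counts nvr1 to nvr3 in the interim prediction model (SAP 4.7.3.1).

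**Working it through.** **1. Reproduce the calendar.** Study day of week w is 1 + 7(w − 1). For PegIFN dosing week y, SAP Table 19 gives 1 + 7(23 + y + z) in Arm 1 and 1 + 7(11 + y + z) in Arm 2, where z is the number of ineligible weeks before PegIFN. With z = 0:

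| | Arm 1 | Arm 2 |
|---|---|---|
| PegIFN Week 19 | 1 + 7×42 = 295 | 1 + 7×30 = 211 |
| PegIFN Week 24 (last planned dose) | 1 + 7×47 = 330 | 1 + 7×35 = 246 |
| OTW1 | 337 (+7) | 253 (+7) |
| OTW2 | 344 (+14) | 260 (+14) |
| Window end | 350 (+20) | 266 (+20) |
| OTW4 | 358 (+28) | 274 (+28) |

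The targets and limits match SAP Tables 2 and 3. OTW1 and OTW2 are inside the window and OTW4 is outside. With a delayed PegIFN start, the window opens at dosing week 19 − z, for example Week 7 for a participant eligible at Eligibility Week 13 (z = 12).

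**2. Apply both readings.** Take an Arm 1 participant who started PegIFN on time, with samples on Days 302, 330, 337 and 344 and all later windows below LLOQ. Day 302 (PegIFN Week 20) is an assumed visit, because the extracted protocol Table 4 is broken; SAP 4.7.2 lists Weeks 20 and 24. The SVR columns apply SAP 4.2.2.2, with planned EoT taken as Week 48.

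| Only value at or above LLOQ | EoT response, *latest* | EoT response, *worst* | SVR, *latest* | SVR, *worst* |
|---|---|---|---|---|
| Day 302 (Week 20) | yes | no | **yes** | **no** |
| Day 330 (Week 24) | yes | no | no | no |
| Day 337 (OTW1) | yes | no | no | no |
| Day 344 (OTW2) | no | no | no | no |
| none | yes | yes | yes | yes |

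EoT response differs in three of the five patterns, SVR in one. That SVR difference applies to any value at or above LLOQ on Days 295–329 (Arm 2: 211–245) followed only by values below LLOQ. A second route is a record labelled missing due to WDE followed by a response in the same window. *Latest* takes the response. *Worst* takes the WDE category, because it ranks ahead of response.

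**3. Relapse.** The PegIFN window closes on Day 350 (266), so a rebound at OTW1 or OTW2 precedes the first day on which relapse can be dated. In the Day 337 row under *latest*, the participant is an EoT responder whose rebound is not a relapse. In the Day 344 row the participant is an EoT non-responder and leaves the group at risk.

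**4. Size.** One participant in an arm of 50 is 1/50 = 2 points. The documents do not say how many are affected. As an illustration, take the Beta(0.5, 0.5) calculation behind SAP Table 12. At n = 50, 17 responders is the minimum for a probability above 65% that the true rate exceeds 30%. The recomputed chances of meeting it at true rates of 30%, 35% and 40% are 31.6%, 61.1% and 84.4%, against the table's 32%, 61% and 84%. Starting from 17 responders:

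| Responders lost (assumed) | Rate | P(true rate > 30%) |
|---|---|---|
| 0 | 34% | 0.735 |
| 1 | 32% | 0.628 |
| 2 | 30% | 0.508 |
| 3 | 28% | 0.386 |

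A single participant at that boundary crosses the 65% mark. This is the sample-size calculation, not the stratified primary model.

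**The case against.** The text leans towards *latest*, with *worst* as a tie-break. That is the main clause of the sentence, and the later windows have their own worst-only rule, which would hardly be needed if EoT worked the same way. Footnote 1 steps back to a preceding value. The relapse start date in SAP 4.1.3 allows for an EoT responder with an earlier non-response in the window. Against this, the SAP version history describes the change to 4.2.2.1 as defining worst-case selection, and the ranked list fits that. The leaning does not settle the rule, and *latest* still puts EoT at OTW2.

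A wide window also has a purpose. Under the assumed visit schedule, participants who start PegIFN late have no scheduled HBsAg sample on the final dosing day; their last one falls 7 to 21 days earlier. That supports the lower limit, but not letting OTW2 displace an available on-treatment value. Protocol 9.4.2 leaves post-treatment windows to the SAP, but itself starts the data at the week treatment ends.

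Two further objections stand. SAP Table 19 applies only to early-termination visits, so Protocol Table 7 is the better source for calling OTW1 and OTW2 off-treatment. And the specified time-to-relapse endpoint runs from the end of GSK3228836; relapse after PegIFN is mentioned in SAP 4.1.3 but only outlined.

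**Conclusion.** The point holds. The window includes two off-treatment visits and its selection sentence has two workable readings. EoT virologic response, as a secondary endpoint and as an interim count, depends on the reading throughout. Primary SVR depends on it only for values at or above LLOQ before planned EoT with nothing but values below LLOQ afterwards, and for WDE-labelled records. The size is about 2 points per participant, for an unknown number of participants.

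Three stronger conclusions that a reader might draw are not supported:
- *EoT response is always read off treatment.* This is true only under *latest*, for participants with an OTW1 or OTW2 sample (or an unscheduled one) after planned EoT.
- *An OTW1 rebound is overlooked in SVR.* SAP 4.2.2.2 makes any value at or above LLOQ from planned EoT onward a non-response under both readings.
- *EoT response and relapse are both understated.* The direction varies. Under *latest*, an OTW2 rebound lowers EoT response, while a Week 24 or OTW1 positive followed by a clear OTW2 raises it.

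The conclusion assumes that planned EoT in SAP 4.2.2.2 means Week 48 or 36, as SAP 4.1 defines it. If it means the analysis window, the boundary of that override is itself unclear. The exact week numbers assume a PegIFN start at Week 1.

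**What to change.** Keep the outer limits in SAP Tables 2 to 4 and replace the selection sentence for the PegIFN EoT window:

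1. Select the latest non-missing assessment up to target +3 days (Day 333 in Arm 1, Day 249 in Arm 2; reference date +3 in Table 4). Apply the worst-case ordering only to results on the same date, and say how a WDE-labelled record is treated.
2. Use an OTW1 or OTW2 value for EoT only if the window holds no earlier value.
3. State that any value at or above LLOQ after the selected EoT assessment, including at OTW1 or OTW2, is an SVR non-response (as in SAP 4.2.2.2) and is the relapse date for PegIFN-EoT responders.
4. Leave the Week 8 and later windows unchanged.

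The +3 days matches the protocol's visit tolerance; the earliest OTW1 day is 334 (250). Simply ending the window at +3 and starting the next one the following day would be worse. The Arm 1 Week 8 window would then open on Day 334, so an OTW1 value could stand in for Week 8 when OTW4 and OTW8 are missed. Participants sampled only at OTW1 or OTW2 would become non-responders.

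The cost is a small programming change, and EoT response shown at earlier interims may need to be re-derived. SAP Table 8 projects all 100 participants at the primary endpoint by the January 2023 review, and SAP v4.0 is dated 22 March 2023. The change should therefore be documented as made after unblinded interim data had been seen.

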4.2. Primary Endpoint Analyses

HBsAg and HBV DNA assessments from the end of treatment analysis window (Week 48 or Week 36 for Arm 1 and Arm 2 respectively) to the off-treatment Week 24 analysis window will be used to analyse the primary endpoint for each arm. The primary analysis for the primary endpoint will be conducted once the database lock has been achieved and the last participant has completed the Week 72 visit.

The primary efficacy endpoint is achieving a sustained virologic response for 24 weeks after the planned end of GSK3228836 and PegIFN sequential treatment in the absence of rescue medication. Sustained virologic response (SVR) is defined as observing HBsAg <LLOQ and HBV DNA <LLOQ at each analysis window in the 24 weeks after the end of sequential treatment. Analysis windows for the post GSK3228836 treatment assessments are defined in Section 4.2.2.1.

An estimation approach with no hypothesis testing will be used to address the primary objective. The primary assessments of interest are the point estimate of SVR rate and 95% credible intervals. In addition, posterior probabilities that the true SVR rate in each treatment arm is greater than a range of clinically meaningful response rates will be provided. The point estimates for SVR will be calculated using a Bayesian probability approach. Comparisons between treatment arms as defined in the key secondary/exploratory objectives will be assessed using probability inference approaches.

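### SAP 4.2.2.1 responder rule 2, applied to Tables 2 and 3, contradicts the SVR window range in SAP 4.2 and Protocol 9.4.2 and leaves a programming risk in the primary endpoint

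*SAP*

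**What the plan says.** SAP 4.2.2.1 applies visit windowing through Tables 2 and 3 and states that "the windowed results will be used to determine the primary endpoint of SVR". The tables are titled "Primary Endpoint Analysis Visit Windows for Arm 1" and "Primary Endpoint Analysis Visit Windows for Arm 2". Each has five rows: End of GSK3228836 treatment, End of PegIFN treatment / EoT, and post-PegIFN Weeks 8, 18 and 24. The first row runs from Day 148 to the earlier of Day 182 and the first PegIFN dosing day in Arm 1. In Arm 2 it runs from Day 64 to the earlier of Day 98 and that day.

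The responder rules follow Table 4. Their lead-in applies when every analysis window has non-missing response information. Rule 2 then reads: "If HBsAg <LLOQ and HBV DNA <LLOQ in each of the analysis windows, then the participant is a responder"; anyone else is a non-responder. Neither the lead-in nor the rule lists windows or exempts a row.

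The parent section, SAP 4.2, gives a range. Data from the EoT window (Week 48 in Arm 1, Week 36 in Arm 2) "to the off-treatment Week 24 analysis window will be used to analyse the primary endpoint for each arm". Protocol 9.4.2 gives the same range. SAP 4.2.2.2 counts a value at or above LLOQ as SVR failure only from planned EoT onward.

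**The concern.** The end-of-GSK3228836 window closes no later than the first PegIFN dosing day. If it counts towards SVR, PegIFN can preserve a response but cannot create one. Protocol 4.2 asks first whether GSK3228836 followed by PegIFN improves on GSK3228836 alone, and SAP 4.2.2 plans a conditional comparison with study 209668. A five-window derivation would remove exactly the responders that PegIFN adds. It would feed the SVR rate in each arm and the comparison of Arm 1 with Arm 2.

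The SAP does not say which text governs if SAP 4.2 and rule 2 disagree. Rule 2 is also the only step-by-step classification rule, so it is the text a programmer is most likely to code from.

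**Working it through.** **1. The passages side by side**

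| Place | Windows or period that decide SVR |
|---|---|
| SAP 4.2.2.1, rule 2 with Tables 2 and 3 | Five if read literally: End of GSK3228836, EoT, post-PegIFN Weeks 8, 18, 24 |
| SAP 4.2, data range | EoT to off-treatment Week 24 |
| SAP 4.2, SVR definition | The 24 weeks after sequential treatment |
| Protocol 9.4.2 | Week of end of treatment to off-treatment Week 24 |
| SAP 4.2.2.2 | Failure for values at or above LLOQ at or after planned EoT |
| SAP 4.7.3.1 (interim) | VR at EoT, sustained to EoT + 24 weeks |
| SAP Table 4 with the same rule 2 | Four: End of Actual treatment, post-treatment Weeks 8, 18, 24 |

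SAP 4.1 defines EoT as the end of both drugs (Week 48/36), so EoT cannot mean the GSK3228836 window.

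**2. Table 4 against Tables 2 and 3**

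SAP Table 19 puts PegIFN dosing Week 24, with no delayed start, at 1 + 7 × (23 + 24) = Day 330 in Arm 1 and 1 + 7 × (11 + 24) = Day 246 in Arm 2. With those days as the Table 4 reference date:

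| Window | Table 4 offset | Arm 1 (ref. 330) | Arm 2 (ref. 246) |
|---|---|---|---|
| End of treatment | −35 to +20 | 295–350 | 211–266 |
| Week 8 | +21 to +76 | 351–406 | 267–322 |
| Week 18 | +77 to +132 | 407–462 | 323–378 |
| Week 24 | +133 to +188 | 463–518 | 379–434 |

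These equal the last four rows of Tables 2 and 3. For a participant dosed exactly to schedule, the only difference is the extra first row. Read literally, the same data could make that participant a responder for the first supplementary estimand and a non-responder for the primary one.

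**3. One participant, two answers**

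Take HBsAg at or above LLOQ in the End of GSK3228836 window, then both markers below LLOQ in the EoT, Week 8, Week 18 and Week 24 windows, with no rescue medication. SAP 4.2, Protocol 9.4.2 and SAP 4.2.2.2 give responder. Rule 2 over all five rows gives non-responder.

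**4. The plan's own figure**

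Inputs from Protocol 9.2 and SAP 5: n = 50 per arm, prior Beta(0.5, 0.5), criterion P(SVR > 20%) > 65%.

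- Posterior with r responders: Beta(r + 0.5, 50 − r + 0.5). P(p > 0.20) is 0.6496 at r = 11 and 0.7657 at r = 12, so 12 are needed, as stated.
- P(X ≥ 12) for X ~ Binomial(50, 0.30) is 0.861. The plan states 86%.
- For the 30% criterion, 17 are needed. P(X ≥ 17) at a true rate of 0.40 is 0.844. The plan states 84%.

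**5. Illustration of literal programming**

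Let f be the share of true responders who clear only on PegIFN. The documents do not give f, so 10% to 50% is an assumption. The rate counted under the literal rule is q = p(1 − f).

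| f | q if p = 0.30 | P(X ≥ 12) | q if p = 0.40 | P(X ≥ 17) |
|---|---|---|---|---|
| 0 | 0.300 | 86% | 0.40 | 84% |
| 10% | 0.270 | 73% | 0.36 | 67% |
| 25% | 0.225 | 45% | 0.30 | 32% |
| 50% | 0.150 | 6% | 0.20 | 1% |

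In counts, 15 true responders out of 50 would be recorded as 13.5, 11.25 or 7.5 on average, against the 12 needed.

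**The case against.** A reader might infer that the SAP, followed as written, makes anyone who clears HBsAg only on PegIFN fail SVR. The documents as a whole do not support that. SAP 4.2 states which windows count, and rule 2 sits beneath it. Protocol 9.4.2, SAP 4.2.2.2 and the interim definition in SAP 4.7.3.1 all start at EoT. Table 4 feeds the same rule without the extra row. SAP 4.2.2.2 has window-level missing-data rules for EoT and later windows but none for the GSK3228836 window, which would be needed if that window decided SVR. The row also has its own purpose: SAP 4.1.3 and 4.3.1.1 use it for response at the end of bepirovirsen and for time to relapse. The intended meaning is therefore clear enough, and all of this stands.

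It does not remove the conflict. The SAP says without exception that the windowed results of Tables 2 and 3 determine SVR, and the table titles say the same. Intent is also weak protection here. In SAP 4.2.5.1 the sponsor records that the modified SVR definition misses its scientific purpose, yet will be programmed as it stands, with the intended version left to notes to file.

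A reader might also infer that the 12-week arm would lose more responders. That would follow only if more of its clearance happens on PegIFN, and the documents give no figure for this. The 20% criterion comes from the sample-size section. The primary analysis is a Bayesian logistic model without hypothesis testing, and SAP 4.2.2 gives 30%, 35% and 40% as example thresholds.

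**Conclusion.** The contradiction is real but limited. Rule 2 and its lead-in, applied to Tables 2 and 3, conflict with SAP 4.2, Protocol 9.4.2 and SAP 4.2.2.2 over whether the end-of-GSK3228836 window counts towards SVR. The weight of the text favours the four windows from EoT to off-treatment Week 24. The fault is therefore a drafting conflict that could produce a wrong primary derivation, not a definition that excludes participants who clear on PegIFN.

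The size of the effect cannot be derived from the documents. The falls from 86% to about 73%, 45% or 6% are illustrations. They assume that 10%, 25% or 50% of responders clear only on PegIFN, that each has a non-missing value at or above LLOQ in the GSK3228836 window and is reclassified, and that the unstratified Beta-binomial criterion of the sample-size section applies. If the four windows are programmed, no figure in the plan changes.

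**What to change.** - In rule 2 and its lead-in, name the windows: EoT and post-PegIFN Weeks 8, 18 and 24 for Tables 2 and 3, and the four matching Table 4 windows for the supplementary estimands.
- Footnote the End of GSK3228836 row in Tables 2 and 3, or move it to its own table, as used only for bepirovirsen end-of-treatment response and relapse (SAP 4.1.3 and 4.3.1.1). A footnote is enough.
- Check the programming specification, and any code already run at the interim analyses, to confirm that SVR uses those four windows.

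The cost is a short SAP wording change and one specification check. It needs no new data and no change to the protocol, the sample size or the model.
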